7.5. Assessment of Adverse Events

7.5.1. Assessment of Adverse Event/Serious Adverse Event Severity

The severity of an AE refers to the extent to which an AE affects the participant's daily activities. Severity will be graded according to the Common Terminology Criteria for Adverse Events (CTCAE), Version 5.0 or later. If an AE is not specified within the CTCAE guidelines, then the AE will be graded according to the definitions in Table 5.

Table 5: Adverse Event Grading Criteria

Grade	Severity	Description
1	Mild	Asymptomatic or mild symptoms; clinical or diagnostic observations only; intervention not indicated.
2	Moderate	Minimal, local, or noninvasive intervention indicated; limiting age-appropriate instrumental ADL ^a
3	Severe or medically significant but not immediately life-threatening	Hospitalization, or prolongation of hospitalization indicated; disabling, limiting self-care ADL ^b
4	Life-threatening consequences	Urgent intervention indicated
5	Death	Death related to AE

ADL=activities of daily living, AE=adverse event.

Note that "severity" is a measure of intensity and that a severe AE is not necessarily an SAE.

Changes in the severity of an AE should be documented to allow assessments of the duration of the events at each level of intensity. AEs characterized as intermittent do not require documentation of onset and end date of each episode. When the intensity of an AE changes more than once a day, the maximum severity for the event should be recorded for that day. If the intensity changes over a number of days, these changes should be recorded separately (eg, as having distinct onset dates on one or more eCRF lines).

^a Instrumental ADL refer to preparing meals, shopping for groceries or clothes, using the telephone, managing money, etc.

^b Self-care ADL refer to bathing, dressing and undressing, feeding self, using the toilet, taking medications, and not bedridden.

AL002 Alector, Inc.

7.5.2. Assessment of Causality

The relationship or association of the study drug or radiotracer, in causing or contributing to the AE will be characterized using the following classification and criteria:

Relationship to Study Drug or Radiotracer	Comment
Related	There is reasonable possibility that the event may have been caused by study drug/ radiotracer (eg, there is a plausible temporal relationship between the onset of the AE and administration of the study drug, and the AE cannot be readily explained by the participant's clinical state, intercurrent illness, or concomitant therapies).
Not Related	The event can be readily explained by the participant's underlying medical condition, concomitant therapy, or other causes, and therefore, the Investigator believes that it is unlikely that a causal relationship exists between the event and study drug or radiotracer.

AE=adverse event; PET=positron emission tomography.

The Investigator should assess causality by answering either "related" or "not related" to the question "Is there a reasonable possibility that the event may have been caused by the study drug" The following factors may be used in consideration of causality assessment:

- Challenge/rechallenge: Did the event abate after study drug was reduced or interrupted? Did the event reappear after study drug was reintroduced?
- Temporal relationship and time to onset plausibility
- Confounding risk factors
- Amount and duration of study drug exposure
- Concomitant medications

7.6. Recording of Adverse Events

7.6.1. Eliciting and Documenting the Adverse Events

At every study visit after screening, participants will be asked a standard nonleading question to elicit any medically related changes in their well-being. They will also be asked if they have been hospitalized, had any accidents, used any new medications, or changed concomitant medication regimens (prescription drugs, herbal products, vitamins, minerals, vaccines, topical medications, and over-the-counter medications). Please refer to Section 6.5.1 for additional AEs and special situations that require immediate reporting to the Sponsor.

Laboratory test values or investigational findings (eg, findings on ECGs, imaging, or examination) outside the normal reference range are not necessarily AEs. Only those that meet the following criteria should be reported as an AE: (1) is confirmed and the Investigator considers clinically significant, or (2) that requires a participant to be discontinued from the study, or (3) that requires a participant to receive treatment. Abnormal laboratory test values or investigational findings reported as AEs should be followed until satisfactory clinical resolution, participant withdrawal of consent, lost to follow-up, or death, whichever comes first. Specific instructions for recording of ARIA-E and ARIA-H as AESI are specified in Section 7.2.1.

AL002 Alector, Inc.

7.6.2. Recording the Action Taken with Study Drug in Response to Adverse Events/Serious Adverse Events

Should the Investigator need to alter the administration of the study drug from the procedure described in the protocol in response to an AE/SAE, then the action taken will be recorded on the AE eCRF page as one of the following options:

- Dose not Changed
- Drug Interrupted
- Drug Withdrawn
- Not Applicable
- Unknown

7.6.3. Recording the Outcome and Follow-up of Participants Reporting an AE/SAE

Outcome of an AE/SAE will be recorded on the AE eCRF as follows:

- Recovered/Resolved
- Recovered/Resolved with Sequelae (with sequelae being a condition that is the consequence of the reported event, and not the event in a lower grade/ severity)
- Not Recovered/Not Resolving
- Fatal
- Unknown

7.7. Reporting Adverse Events

7.7.1. Adverse Events and Serious Adverse Events Reporting

Regardless of cause or relationship to study drug, all AEs/SAEs that occur after a participant signs the informed consent until the end of study participation, regardless of clinical significance or of the suspected relationship of the AE to study drug and/or radiotracer, should be reported by the Investigator. All unresolved AEs and/or SAEs will be followed through their resolution, or until the participant returns to his or her baseline condition, or is lost to follow-up or dies of another cause. Additionally, SAEs considered related to the study drug or radiotracer, which occur at any time during the study, should be reported by the Investigator, regardless of the AE/SAE collection window. Definitions pertaining to AEs are provided in Section 7.1.

Information to be collected includes but is not limited to the following:

- Event term
- Time and date of onset of event
- Investigator-specified assessment of severity and relationship to study drug or radiotracer
- Time and date of the end of the event or the date on which the event changes severity

Alector, Inc.

- All serious criteria (if applicable)
- Any required treatment or evaluations
- Event outcome

In the event of any SAE reported or observed during the study, the site is required to complete the AE eCRF within the EDC system, including the event seriousness criteria, within 24 hours of becoming aware of the event or aware of substantive new information relating to the event.

Please note two additional scenarios requiring 24-hour reporting to the Sponsor:

- 5. AEs assessed as related to the radiopharmaceutical, Neuraceq[®] (florbetaben 18F injection). **Please note:** if the site's imaging facility is located outside of the institutional facility, please ensure the imaging lab is aware of this requirement.
- 6. Special situations (eg, overdose, occupational exposure, medication error) associated with Neuraceq® or the Alector study drug regardless of whether the special situation is associated with an AE and regardless of the Investigator's causality assessment of the event to the radiotracer or Alector study drug.

If the EDC system is not available, a paper Serious Adverse Event Report Form should be used and emailed to according to the instructions provided in the Study Specific Regulatory Binder. Once the EDC system becomes available, SAEs reported using a paper Serious Adverse Event Report Form should be entered in the EDC system. The interval for which AEs are reported as described above also applies to SAE reporting.

The participant's condition will be followed by the Investigator or designated Subinvestigator, as described in Section 7.9. If unscheduled visits are required, the participant will be asked to return to the study site for further follow-up. As additional information becomes available, such as hospital discharge notes and participant medical records, the Investigator or designee will update the SAE eCRF and other relevant documentation pertaining to the SAE, and these updates will be submitted to the Sponsor within 24 hours of knowledge.

- Alector is responsible for notifying applicable regulatory agencies of any unexpected fatal or life-threatening suspected adverse reaction as soon as possible, but in no case later than 7 calendar days after the Sponsor's initial receipt of the information. In addition, Alector must notify the applicable regulatory agencies and all participating Investigators in an IND safety report of potential serious risks, from clinical trials or any other source, as soon as possible, but in no case later than 15 calendar days after Alector determines that the information qualifies for reporting.
- It is the Investigator's responsibility to report all SAEs to Alector (covered in Section 11.6) in compliance with current regulations and it is Alector's responsibility to ensure all safety reporting obligations are carried out in compliance with current legislation for expedited reporting of SAEs (including suspected unexpected serious adverse reactions).

The MedDRA Version 23.0 or later will be used by Alector to code all AEs.

AL002 Alector, Inc.

7.8. Safety Monitoring

For medical emergencies, contact Sponsor's Medical Monitor or designee:

PPD Safety Hotline

North America:

• Europe, Middle East, and Africa/Asia-Pacific Region:

The Medical Monitor will review AE reports, compiled by Data Management, as described in the Medical Monitoring Plan. The Medical Monitor will review blinded study data on enrollment, abnormal laboratory results and protocol deviations. These reports will collectively be known as the Medical Monitoring Report.

7.9. Follow-Up of Adverse Events and Serious Adverse Events

All AEs, SAEs, and AESI that are deemed related, possibly related, or probably related to study drug must be followed until resolution, the condition stabilizes, the event is otherwise explained, the participant dies of another cause, or is lost to follow-up. The Investigator is responsible for ensuring that follow-up includes any supplemental investigations that may be indicated to elucidate as completely as practical the nature and/or causality of the AE/SAE/AESI. This may include additional laboratory tests or investigations, histopathological examinations, or consultation with other health care professionals.

The Sponsor may request that the Investigator perform or arrange for the conduct of supplemental measurements and/or evaluations. If a participant dies during participation in the study or during the protocol-defined follow-up period, the cause of death should be reported as a SAE and the Sponsor should be provided with a copy of any postmortem findings, including histopathology.

All AEs, AESI, and SAEs that have not resolved by the end of the study, or that have not resolved upon discontinuation of the participant's participation in the study, must be followed up until any of the following occurs:

- The event resolves.
- The event stabilizes.
- The event returns to baseline, if a baseline value is available.
- The participant withdraws consent.
- The participant dies.
- The event can be attributed to agents other than the study drug, [¹⁸F]MK-6240 radiotracer, or to factors unrelated to study conduct.
- It becomes unlikely that any additional information can be obtained (participant lost to follow-up or medical records are not received after demonstration of due diligence with follow-up efforts).

AL002 Alector, Inc.

After the protocol-defined follow-up period, if the Investigator becomes aware of any SAE that is assessed as related to an Alector study drug or radiotracer, the SAE must be reported to Alector within 24 hours of site awareness.

7.10. Infusion Reactions

Signs or symptoms of AEs during the infusion will be carefully monitored and treated according to standard of care. In addition, in the event of an infusion reaction, serum samples of PK and ADAs should be obtained, as well as a plasma sample for cytokine, etc. See Section 14.3 for information on the management of infusion-related reactions.

7.11. Amyloid-Related Imaging Abnormalities

Amongst the brain abnormalities detected on MRI are ARIA which are believed to reflect leakage of proteinaceous fluid or other blood products into the leptomeninges or brain parenchyma. The term ARIA was originally coined to describe specific brain abnormalities seen on MRI in anti-amyloid clinical trials. Although MRI findings potentially caused by AL002 may or may not be related to disruption/mobilization of, or a reaction to, amyloid species in the brain parenchyma or vasculature, the term ARIA will be used in this protocol to describe such findings until the biological mechanism is better understood. Specifically, according to the convention developed to describe ARIA occurring in clinical trials of anti-amyloid immunotherapies, ARIA-E will refer to MRI findings of vasogenic edema and leptomeningeal/sulcal effusion, and ARIA-H will refer to MRI findings of cerebral microhemorrhages, leptomeningeal hemosiderosis (also known as superficial siderosis of the CNS) and cerebral macrohemorrhages.

For the purpose of this protocol, four categories of ARIA will be tracked (see Section 7.2.1 for recording of AESIs of ARIA). These categories are ARIA-E, ARIA-H cerebral microhemorrhages, ARIA-H leptomeningeal hemosiderosis, and ARIA-H cerebral macrohemorrhages. Symptoms associated with ARIA-H and ARIA-E will be captured as separate AEs on the AE eCRF and linked to the applicable ARIA AE line number. All clinical signs and symptoms that are identified as associated with an ARIA finding will be entered as separate AEs on the AE eCRF. Based on evaluation of the participant for signs and symptoms, and review of safety findings by the Sponsor that possibly indicates the presence of ARIA, the Sponsor may request an unscheduled MRI be obtained.

To maintain consistency of reporting across clinical sites, findings of ARIA-E or ARIA-H on MRI are determined by the MRI Central Reader by radiologists with expertise in assessing for ARIA and other abnormalities on brain MRI. ARIA-E, ARIA-H and other findings are documented on and reported to the sites with the BMW report (see Section 6.5.12). The BMW provided by the Central Reader after each MRI examination scores ARIA-E (parenchymal vasogenic edema, leptomeningeal/sulcal effusion) according to: extent, location, number of sites involved, radiographic severity (mild, mild+, moderate, moderate+, severe) (Table 6) and changes since prior MRI exams. ARIA-E findings typically resolve radiographically and will be noted as such on the BMW of follow-up MRI scans. The BMW also documents occurrence and characteristics (location, size, number) of ARIA-H (parenchymal microhemorrhages and leptomeningeal hemosiderosis and macrohemorrhages).

Overall, ARIA-H radiographic severity is defined as the worst individual radiographic severity for microhemorrhages, leptomeningeal hemosiderosis or macrohemorrhages (eg, if there are

Alector, Inc.

4 incident microhemorrhages, 1 incident areas of leptomeningeal hemosiderosis and no macrohemorrhages, then ARIA-H is rated as "Moderate") (Table 6).

Table 6: ARIA-E and ARIA-H Radiographic Severity Scales

ARIA-E Characterization:		Severity/Grade	
<5 cm monofocal		Mild (Grade 1)	
<5 cm multifocal		Mild+ (Grade 2)	
5-10 cm monofocal	N	Moderate (Grade 3)
5-10 cm multifocal	Moderate+ (Grade 4)		
>10 cm monofocal/multifocal	Severe (Grade 5)		
Incident ARIA-H:	Mild	Moderate	Severe
microhemorrhages	1-4	5-9	10 or more
Areas of leptomeningeal hemosiderosis	NA	1	2 or more
macrohemorrhages	NA	NA	1 or more

ARIA-E=amyloid-related imaging abnormalities-edema; ARIA-H=amyloid-related imaging abnormalities-hemosiderin deposits; NA=not applicable.

ARIA-H findings very rarely resolve radiographically; it is more typical for ARIA-H findings to stabilize radiographically. Radiographic stabilization of an ARIA-H finding is defined as when a follow-up MRI scan shows no increase in number/size/extent of previously seen cerebral microhemorrhages, leptomeningeal hemosiderosis and cerebral macrohemorrhages.

7.11.1.1. Schedule of MRI Surveillance for ARIA

Surveillance for treatment-emergent ARIA will be accomplished with post-randomization MRI scans as follows: MRIs to be performed 5-10 days before Dose 2 (Day 29), Dose 3 (Day 57), and Dose 4 (Week 13), and 5-10 days before doses at all subsequent visits with MRI (Weeks 25, 49, 73, 97) (see Section 14.1). The Sponsor may request that additional unscheduled MRIs be performed for the detection and follow-up of ARIA.

If new or worsening ARIA is observed on any of these post-randomization MRIs, dosing should be managed as prescribed in the Dosing Guidelines for ARIA (see Table 7).

7.11.1.2. Participant Follow-up for ARIA Events

Participants with new or worsening radiographic evidence of ARIA on post-baseline MRI scans should be evaluated for neurological signs or symptoms during an unscheduled visit.

Investigators should comprehensively review the BMW for the presence of ARIA or other abnormalities. When ARIA has been detected, follow-up BMWs should be reviewed for radiographic evolution/resolution/stabilization of findings. Investigators suspecting ARIA that has not been detected by the MRI Central Reader should contact the Medical Monitor. For instance, if a local radiologist detects a faint area of vasogenic edema or microhemorrhage, which was not documented in the BMW, the Investigator should contact the Medical Monitor.

Alector, Inc.

If participants are determined to have ARIA-related symptoms or signs, the Medical Monitor should be contacted within 48 hours. Investigators should be aware of the symptoms most commonly observed in participants with symptomatic ARIA. ARIA-related symptoms are typically non-localizing such as headache, confusion, visual changes, dizziness, nausea, and gait difficulty. However, in some cases, focal neurological deficits (eg, visuospatial difficulty, aphasia, and apraxia) may occur. Serious ARIA symptoms can include encephalopathy, stupor, seizures, and status epilepticus (Cummings 2023, Cogswell 2022).

Participants with asymptomatic ARIA-E may be observed; for participants with mild or moderate symptomatic ARIA-E, the use of oral or IV steroids may be considered (see Table 7). In the case of severe symptomatic ARIA-E, it is recommended to hospitalize the participant for close observation and consider the use of IV steroids such as high-dose dexamethasone or a similar agent.

All new cases of ARIA-E and/or new cases of ARIA-H will require unscheduled MRI scans every 4-6 weeks until ARIA-E has resolved and/or until ARIA-H has stabilized without new findings. In addition, the Sponsor may request that additional unscheduled MRIs be performed for the detection and follow-up of ARIA.

An Amyloid PET scan should be requested after the first occurrence of ARIA-E and/or ARIA-H for those participants who have opted-in to have longitudinal Amyloid PET performed. An unscheduled LP for CSF analysis and plasma may be requested, if not contraindicated, after any occurrence of ARIA-E and/or ARIA-H.

Participants in Part 1 with MRI evidence of ARIA at the Day 15 or Day 43 MRI will be discontinued from study drug administration. Participants in Part 1 with ARIA after Day 43 and participants in Part 2 with MRI evidence of ARIA at any visit will be managed according to the guidelines in Table 7.

AL002 Alector, Inc.

Table 7: Dosing Guidelines for ARIA

Finding	Asymptomatic/Symptomatic	Action	
Milda ARIA-E	Asymptomatic or Symptomatic	Suspend dosing until resolution of ARIA-E or	
Moderate ^b ARIA-E	Asymptomatic or Symptomatic	stabilization of ARIA-H. After resolution (ARIA-E) and/or stabilization (ARIA-H), if	
Severe ARIA-E	Asymptomatic or Symptomatic	participant dosing is restarted, they must receive the same dose they received immediately prior	
Mild or Moderate ARIA-H	Asymptomatic	to the ARIA-E/ARIA-H findings and continue on that dose for the remainder of the study. After resuming dosing, 5-10 days before their second post-resumption dose, participants must undergo an unscheduled MRI that must be assessed by the Central Reader for ARIA-E/H before the next dose is administered.	
		For mild or moderate symptomatic ARIA-E the use of oral or IV steroids can be considered.	
		For severe symptomatic ARIA-E it is recommended to hospitalize the participant for close observation and consider the use of IV steroids such as high-dose dexamethasone or a similar agent.	
Mild or Moderate ARIA-H	Symptomatic	Permanently discontinue treatment	
Severe ARIA-H	Asymptomatic or Symptomatic	Permanently discontinue treatment	
Serious ^c ARIA-E or Serious ARIA-H	Symptomatic	Permanently discontinue treatment	
Serious ^c ARIA-E or Serious ARIA-H	Asymptomatic	Suspend dosing until resolution of ARIA-E or stabilization of ARIA-H. After resolution (ARIA-E) and/or stabilization (ARIA-H), if participant dosing is restarted, they must receive the same dose they received immediately prior to the ARIA-E/ARIA-H findings and continue on that dose for the remainder of the study. After resuming dosing, 5-10 days before their second post-resumption dose, participants must undergo an unscheduled MRI that must be assessed by the Central Reader for ARIA-E/H before the next dose is administered.	
A second occurrence of ARIA-E after full resolution of a prior occurrence of ARIA-E	Asymptomatic or Symptomatic	Permanently discontinue treatment	

ARIA-E=amyloid-related imaging abnormality-edema; ARIA-H=amyloid-related imaging abnormality-hemosiderin deposits; MRI=magnetic resonance imaging.

^a Mild includes 'mild' and 'mild+', as scored on the BMW from the Central Reader.

^b Moderate includes 'moderate-' and 'moderate+', as scored on the BMW from the Central Reader.

^c Meets criteria for a SAE.

AL002 Alector, Inc.

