7.3. Definition of Serious Adverse Events

An SAE is defined as any AE that fulfills one or more of the following criteria:

- Results in death
- Is immediately life-threatening
- Requires inpatient hospitalization or prolongation of existing hospitalization
- Results in persistent or significant disability/incapacity
- Results in congenital anomaly/birth defect
- Is an important medical event that may jeopardize the participant or may require medical intervention to prevent one of the outcomes listed above.

Important medical events that may not meet one of the above criteria could be considered a SAE by the Investigator when, based upon appropriate medical judgment, they are considered clinically significant and may jeopardize the participant, or may require medical or surgical intervention to prevent one of the outcomes listed above.

An AE is considered "life-threatening" if, in the opinion of either the Investigator or the Sponsor, its occurrence places the participant at immediate risk of death. It does not include an AE that, had it occurred in a more severe form, might have caused death.

7.3.1. Protocol Specific Disease Progression Adverse Event and Serious Adverse Event Reporting Requirements

Disease progression in this study is measured via the CDR-SB. Changes in these scores that are consistent with the expected rate of progression of the underlying disease should not be recorded as AEs.

However, symptomatic deterioration or events that are judged by the Investigator to be inconsistent with normal disease progression or are considered related to study drug should be reported as AEs, and if any of the "serious" criteria are met, it must be reported as an SAE.

Please note that the term "disease progression" should not be reported, but rather the clinical manifestation(s) with applicable descriptors should be captured on the AE eCRF page.

7.4. Definition of Clinical Laboratory Abnormalities and Other Abnormal Assessments as Adverse Events/Serious Adverse Events

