#### 6.3.7.2.2 Severity Definition

Individual radiographic severity for microhemorrhages, leptomeningeal hemosiderosis and macrohemorrhages is defined in Table 6-4. ARIA-H radiographic severity is defined as the worst individual radiographic severity among microhemorrhages, leptomeningeal hemosiderosis and macrohemorrhages for an MRI scan as captured in its BMW. If any macrohemorrhages are present at an MRI scan, then the ARIA-H radiographic severity is severe. If macrohemorrhages are absent at an MRI scan, then the worse severity between microhemorrhages and leptomeningeal hemosiderosis will be the ARIA-H radiographic severity. For example, if there are 4 incident microhemorrhages, 1 incident areas of leptomeningeal hemosiderosis and no presence of macrohemorrhages on a BMW, ARIA-H is rated as "Moderate".

Table 6-4. Definition for Individual Radiographic Severity related to ARIA-H

Incident (CFB) Findings	Mild	Moderate	Severe
Number of microhemorrhages	1-4	5-9	10 or more
Areas of leptomeningeal hemosiderosis		1	2 or more
Presence of macrohemorrhages	_	_	Yes

Protocol No. AL002-2 Last Revision Date: 12 Aug 2025

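### ARIA dosing table (Protocol Table 7): asymptomatic ARIA-H that is both radiographically severe and serious matches a permanent-stop row and a suspend-with-optional-restart row, and nothing says which governs

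*Protocol*

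**What the plan says.** Protocol Section 7.11.1.2, Table 7, is the dosing rule for ARIA. Two of its rows matter here.

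- *Severe ARIA-H*, asymptomatic or symptomatic: "Permanently discontinue treatment".
- The row for serious events of either ARIA type that cause no symptoms says: "Suspend dosing until resolution of ARIA-E or stabilization of ARIA-H. After resolution (ARIA-E) and/or stabilization (ARIA-H), if participant dosing is restarted". The row then sets the restart dose (the one given just before the finding) and an extra MRI before the second resumed dose.

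The two row labels measure different things. Footnote c defines serious as "Meets criteria for a SAE". Severe is an imaging grade: "Overall, ARIA-H radiographic severity is defined as the worst individual radiographic severity for microhemorrhages, leptomeningeal hemosiderosis or macrohemorrhages" (Section 7.11, Table 6). SAP Section 6.3.7.2.2 adds: "If any macrohemorrhages are present at an MRI scan, then the ARIA-H radiographic severity is severe". Protocol Section 7.5.1 also keeps severity apart from seriousness.

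A serious event need not cause symptoms. One SAE criterion in Section 7.3 reads: "Is an important medical event that may jeopardize the participant or may require medical intervention to prevent one of the outcomes listed above".

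In Section 14.3, Table 10, the Treatment column for Grade 3 or 4 infusion reactions ends study drug for all of them. The next column bars redosing only after a serious Grade 3 or any Grade 4 reaction, and leaves redosing after a nonserious Grade 3 reaction to the Medical Monitor.

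**The concern.** ARIA is the trial's identified risk, and Table 7 is applied at approximately 90 sites. A site with a silent macrohemorrhage that it has reported as an SAE finds the event in two rows with different actions. Since it is handling an SAE, the serious row is a natural place to look, and that row sets out how to resume dosing.

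The bar for resuming is low. For ARIA-H, "Radiographic stabilization of an ARIA-H finding is defined as when a follow-up MRI scan shows no increase in number/size/extent". A bleed that has merely stopped growing meets it. If the serious row is taken to govern, a participant could be re-exposed at the same dose after an event that another row says must end treatment. The same bleed, if not classed as serious, would mean a mandatory stop.

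**Working it through.** The documents give no figure to reproduce on this point. The check is to list every combination and read off the matching rows.

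**ARIA-H.** 3 grades × 2 symptom states × 2 seriousness states = 12 combinations. The 6 nonserious ones each match one row. The 6 serious ones match two:

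| Grade | Symptoms | Severity row | Serious row | Result |
|---|---|---|---|---|
| Mild | No | Suspend | Suspend | Agree |
| Moderate | No | Suspend | Suspend | Agree |
| Severe | No | **Stop** | **Suspend** | **Conflict** |
| Mild | Yes | Stop | Stop | Agree |
| Moderate | Yes | Stop | Stop | Agree |
| Severe | Yes | Stop | Stop | Agree |

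So 1 of 12 combinations receives opposing actions.

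**What the serious asymptomatic row adds.** For a first event it covers 3 ARIA-E grades and 3 ARIA-H grades. All 3 ARIA-E grades and 2 of the ARIA-H grades are already suspended by their severity rows. Its only distinct effect, 1 case of 6, is to soften the stop for severe ARIA-H. A reader who tries to give every row a purpose is therefore led to the less safe answer.

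**ARIA-E.** 3 grades × 2 symptom states × 2 seriousness states × first or second occurrence = 24 combinations. Those matching both a suspend row and a stop row are the first occurrences that are serious and symptomatic (3) and all second occurrences (3 × 2 × 2 = 12), so 3 + 12 = 15. In each of these the stop comes from the serious symptomatic row or the second-occurrence row, which read naturally as escalations of the severity rows. That precedence is sensible but unwritten. In the ARIA-H cell the added row is the lenient one, so the same logic gives the wrong direction.

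**Is the conflict settled elsewhere in the Protocol?**

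- Section 4.3.1 lets the Investigator or sponsor stop study drug at any time and lists serious AEs as a possible reason. Its ARIA item refers back to Section 7.11.
- Section 7.2 alerts the Medical Monitor to each AESI, and Section 7.7.1 requires SAE entry within 24 hours. Neither ranks the rows.
- The 48-hour contact in Section 7.11.1.2 is triggered by symptoms or signs, so it does not reach an asymptomatic case.
- In Part 1, Section 3.1.11 (dose-limiting events through Day 43) and the Day 15/Day 43 MRI rule in Section 7.11.1.2 largely settle the action as a stop. Part 2, and Part 1 after Day 43, remain.

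**How soon could a restart come?** New cases "will require unscheduled MRI scans every 4-6 weeks until ARIA-E has resolved and/or until ARIA-H has stabilized without new findings". Take detection 5 to 10 days before dose day D (Section 7.11.1.1), a read within 5 days (Section 6.5.12) and the 4-weekly dosing grid.

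- Follow-up MRI at 28 days: performed D+18 to D+23, read by D+23 to D+28, dose at D+28. One dose missed.
- Follow-up MRI at 42 days: performed D+32 to D+37, read by D+37 to D+42, dose at D+56. Two doses missed.

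If the first follow-up scan shows stabilization, the two rows differ by a permanent stop against 1 or 2 missed doses.

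**The case against.** The strongest reply is that only one course satisfies both rows. The severe row is unconditional and names asymptomatic cases. The serious row never instructs a restart; it sets conditions in case one happens. Suspending and not resuming obeys both, whereas resuming breaches the severe row. This stands. A reader might infer that the table orders sites to restart, or that a site which restarts is fully compliant; the documents support neither. What remains is that one row contains a restart pathway for an event that another row says must end treatment, with no statement that the pathway is closed.

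A second reply is oversight. The event is both an SAE and an AESI, so the sponsor and Medical Monitor learn of it quickly. That makes an unnoticed restart less likely, but it does not tell them which row to apply.

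A third concerns the remedy. A general rule that the strictest matching row applies looks harmless but is not. Table 7 suspends for severe symptomatic ARIA-E and, in the same cell, recommends hospitalization. Inpatient hospitalization is an SAE criterion in Section 7.3. Under a general rule, following the recommendation would turn most such events into permanent stops and largely empty the suspend provision. The objection is right, and the fix should be narrower.

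On Table 10, the redosing column can be read as an exception needing approval, and the likely error is the cautious one. It is a minor point.

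**Conclusion.** The overlap is real and should be corrected. It is a contradiction inside a safety stopping rule, confined to one ARIA-H cell of 12: severe, asymptomatic and serious. It rests on the Table 6 and SAP definition of severe, on footnote c, and on an asymptomatic bleed being able to qualify as an SAE, which Section 7.3 allows.

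The size in participants is unknown. The 1 of 12 and 15 of 24 are table combinations, and the documents give no event counts.

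A reader might also infer harm to the primary analysis, because under SAP Section 6.2.1.2 CDR-SB values more than 37 days after premature discontinuation are treated as missing. The documents do not support that as a consequence of the ambiguity. The loss follows from any permanent stop, which the severe row already requires, and the supportive estimand in SAP Section 6.2.1.3 keeps all on-study data. The effect on the primary data is negligible, and sample size, power and alpha are untouched.

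**What to change.** 1. **Table 7, main change.** Either limit the serious asymptomatic row to serious ARIA-E and serious mild or moderate ARIA-H, or add a sentence that severe ARIA-H always ends treatment, whether or not it is serious.
2. **Table 7, ARIA-E.** State that the serious symptomatic row and the second-occurrence row override the ARIA-E severity rows. Before this is written, the sponsor should confirm that it is intended for severe symptomatic ARIA-E, given that the recommended hospitalization itself makes the event an SAE. If it is not intended, an exception is needed there.
3. **Table 10, minor.** Bring the Treatment column into line with the redosing column: permanent discontinuation for serious Grade 3 and any Grade 4, and dosing held after nonserious Grade 3 unless the Medical Monitor approves redosing. If a stop for all Grade 3 reactions is meant, delete the redosing sentence instead.

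These are wording changes for a clarification letter or the next amendment, with no new visits, procedures or data. The cost of the main change is that the rare participant with serious, severe, asymptomatic ARIA-H who might have restarted would stop study drug.
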